#### **6.3.6.5 Pregnancy**

Pregnancy occurring in a female subject during the study period will be documented in the subject's source documents and reported on a Pregnancy Report form to the SAE hotline and to the IRB/IEC by the investigational staff within 1 working day of their knowledge of the event. Pregnancy itself is not an AE; it should be reported for tracking purposes. The investigator or designee will discontinue the pregnant subject from the treatment aspects of the study (PK testing, biomarker testing, and IV GMI-1070 administration), continue to follow her per protocol for safety outcomes only, and advise her to seek prenatal care and counseling from her primary care provider. Data on fetal outcome and breast-feeding will be collected for regulatory reporting and drug safety evaluation.

If the pregnancy is due to a subject's failure to comply with the contraceptive requirements of this protocol, this should also be documented as a protocol deviation.

Complications of pregnancy or congenital abnormalities in the newborn child will be reported appropriately as AEs.

The site clinical staff will request the pregnant subject to notify the site of the outcome of the pregnancy (ie, birth, loss, or termination). To help ensure this, the site clinical staff will follow-up with the subject until the end of pregnancy, with the subject's consent. This request and the subject's response will be documented in the subject's source document.

## 6.4 Pharmacokinetics Sampling

Plasma PK samples will be obtained prior to first dose and at 14 different timepoints following the start of the first dose for a total of 15. These timepoints have been selected so as to describe the time course of optimal plasma levels of GMI-1070, samples being obtained more frequently when plasma concentrations are changing rapidly and less frequently when they are changing more slowly. Although 15 different sample timepoints are identified, it is not practical to obtain that many samples from each individual in this target population, as a result of limited venous access and preexisting anemia. Thus, a "sparse sampling" approach, coupled with population PK methods, has been adopted to decrease the number of samples obtained from each subject. Each subject will be sampled 9 times from a pre-determined subset of the complete collection of timepoints. Subjects will be assigned to 1 of 2 sampling groups (Table 8 and Table 9). This approach – sparse sampling coupled with population PK analysis methods – is widely accepted as appropriate for determining PK parameters in clinical studies.

Beginning at the start of the second or third dose, urine will be collected over 12 hours for each subject. A sample of the urine collected will be tested to determine the concentration of GMI-1070. The urine concentration and volume will be used to determine the amount excreted over the collection period.

Samples will be shipped according to the Sponsor's instructions to the bioanalytical laboratory (refer to the Study Reference Manual for contact information). Specific details for sample handling, storage, and shipping may be found in the Study Reference Manual. Once PK testing is complete on these samples, they will be used for biomarker analysis. When all study-related testing is complete, the samples will be destroyed.

### *Pharmacokinetics Sampling*

Total plasma sampling for PK will be performed at the following times during the period of hospitalization. For each set of doses, study staff should choose 1 of the doses for sampling based on timing of dose and staff availability:

#### **Visit 1**

##### *Pre Loading Dose:*

- Pre dose of study drug

##### *Post Dose 2 or 3:*

- 30 ± 10 minutes, and 1 ± 0.25, 2 ± 0.25, 4 ± 1, 8 ± 2, and 12 ± 2 hours post initiation of dosing
- Urine samples for PK will be collected for 12 hours starting immediately after administration of dose 2 or 3

***Immediately Pre Dose 4 or 5:***

- Pre dose of study drug

***Immediately Pre Dose 6 or 7:***

- Pre dose of study drug

***Post Dose 6 or 7 (if still receiving study drug):***

- 30 ± 10 minutes, and 1 ± 0.25, 2 ± 0.25, 4 ± 1, and 8 ± 2 hours post initiation of dosing

**Visit 2*****Post Last Dose:***

- 36 ± 12 hours post initiation of last dose

Subjects will be divided into 2 groups (Group A or B) based on randomization for a sparse PK sampling plan. The group assignment will determine the sampling time for each subject. Each subject will have 9 samples of 3 mL blood drawn per sample; and each subject will have urine collected. Biomarker testing will be done on the plasma remaining from sparse PK samples.

**Table 8. Group A Schedule of Sparse Pharmacokinetics, Biomarkers, and Intravital Microscopy Sampling Assessments**

	Visit 1															Visit 2	
	Pre-Loading Dose	Loading Dose	Post Dose 2 or 3						Immed. Pre Dose 4 or 5	Immed. Pre Dose 6 or 7	Post Dose 6 or 7 (if still receiving study drug)					Post Last Dose	
			Min	Hour							Min	Hour					
				30± 10	1± 0.25	2± 0.25	4± 1	8± 2				12 ± 2 	30± 10	1± 0.25	2± 0.25		4± 1
ALL SITES																	
PK, Group A	✓		✓		✓		✓		✓	✓		✓		✓		✓	
Urinalysis			✓ 														
SELECTED SITES																	
IVM and Additional Biomarkers	✓		✓			✓	✓		✓	✓						✓	

**Table 9. Group B Schedule of Sparse Pharmacokinetics, Biomarkers, and Intravital Microscopy Sampling Assessments**

	Visit 1															Visit 2	
	Pre-Loading Dose	Loading Dose	Post Dose 2 or 3						Immed. Pre Dose 4 or 5	Immed. Pre Dose 6 or 7	Post Dose 6 or 7 (if still receiving study drug)					Post Last Dose	
			Min	Hour							Min	Hour					
				30± 10	1± 0.25	2± 0.25	4± 1	8± 2				12 ± 2 	30± 10	1± 0.25	2± 0.25		4± 1
ALL SITES																	
PK, Group B	✓			✓		✓		✓	✓		✓		✓		✓	✓	
Urinalysis			✓ 														
SELECTED SITES																	
IVM and Additional Biomarkers	✓		✓			✓	✓		✓	✓						✓	

 Must be drawn before next dose.

 Collected for 12 hours on the day of Dose 2 or 3, starting at beginning of dose.

 Sites capable of doing IVM and additional biomarker tests will do so.

## **6.5 Clinical Activity Evaluations**

### **6.5.1 Pain Management and Medications**

Pain will also be assessed via the amount and duration of IV opioid, and IV NSAID use, and the time to transition to oral pain medications.

### **6.5.2 Complications of Disease**

Complications of VOC will be assessed by recording the occurrence of acute chest syndrome, transfusions, stroke, death, etc, during the study.

### **6.5.3 Biomarkers of Adhesion and Inflammation**

Markers of adhesion and inflammation will be tested on plasma samples taken for PK sampling, using the left-over sample once PK testing is complete. Biomarker tests may include soluble selectins, integrins, cytokines, and other related markers. Once PK and biomarker testing for this study is complete, samples will be destroyed.

High sensitivity CRP (hsCRP), which can also be considered a biomarker, will be tested as part of the clinical lab sampling done at the investigative site, as noted under “clinical laboratories” on Table 1.

### **6.5.4 Optional Site-Specific Biomarkers**

In a subset of subjects at sites capable of performing these tests, IVM testing for microvascular blood flow, and blood sampling for other biomarkers of adhesion and inflammation, may be performed at the times specified in Table 8 and Table 9 as feasible. Where applicable, this will be described in a site-specific addendum to the Study Reference Manual. This testing will not proceed until the local IRB/IEC has approved an informed consent form detailing the specific procedures.

For this subset of subjects, IVM and additional biomarker sampling may be performed at the following times, as feasible:

#### **Visit 1**

##### ***Pre Loading Dose:***

- Pre-dose

##### ***Post Dose 2 or 3:***

- 30 ± 10 minutes post initiation of dose 2 or 3
- 4 ± 1, and 8 ± 2 hours, post initiation of dose 2 or 3

##### ***Pre Doses 4 or 5:***

- Immediately prior to dosing

***Pre Doses 6 or 7:***

- Immediately prior to dosing

**Visit 2*****Post Last Dose:***

- 36 ± 12 hours post last dose

Sampling may continue for up to 2 days post last dose, as feasible. Additional sampling times may be considered on a per-site basis. For sites participating in this portion of the study, all IVM and additional biomarker sampling to be considered on a per-site basis will be described in detail in the Study Reference Manual for that site.

**6.5.5 Healthcare and Resource Utilization**

Healthcare and resource utilization will be assessed during hospitalization via the following:

- Time to readiness for discharge (per subject and physician)
- Rate of transfer to ICU
- Diagnosis leading to transfer to ICU
- Duration of hospital length of stay
- Oxygen use
- IV antibiotic use
- Number and type of transfusions

Readiness for hospital discharge will be determined by asking the question, “Is your pain now at the level where you can manage it at home with oral medications?” This question will be asked with pain score assessments once IV opioid doses are being weaned. The time at which the subject responds in the affirmative will be noted in the source record. The time at which the physician caring for the subject and/or the investigator agrees with a similar statement (“the subject’s pain is at a level where it can be managed at home on oral medications”) will also be noted in the record.

**7 DATA COLLECTION AND DATA MONITORING****7.1 Data Management**

Data from CRFs and other external data will be entered into a clinical database as specified in the CRO’s data management plan. Quality control and data validation procedures will be applied to ensure the validity and accuracy of the clinical database.

Data from CRFs and other external data will be reviewed and checked for omissions, apparent errors, and values requiring further clarification using computerized and manual procedures. Data queries requiring clarification will be documented and returned to the investigational site for resolution. Only authorized personnel will make corrections to the clinical database, and all corrections will be documented in an audit trail.

## **7.2 Data Monitoring**

After study initiation, the investigational site will be visited by the CRO on behalf of the Sponsor to review the CRFs and source documents for completeness, accuracy, protocol compliance, subject safety, and adherence to guidelines outlined in the Study Reference Manual. The CRO representative will highlight any discrepancies found between source documents and the completed CRFs and ensure that appropriate site personnel address the discrepancies. When a discrepancy results in corrected CRF data, the correction will be initialed and dated on the CRF. Uniform procedures will be discussed at the site initiation. In addition, the Sponsor may visit the site on occasion to review study documents and procedures.

## **8 STATISTICAL ANALYSIS**

The statistical analyses described in this section will be performed as further outlined in the Statistical Analysis Plan (SAP), which will be finalized prior to completion of the clinical portion of the study and will be included in the Clinical Study Report for this protocol. The SAP will give a detailed description of the summaries and analyses (primary and secondary) that will be performed. Changes from analyses planned in the protocol will be documented in the SAP. If changes to principal features stated in the protocol are required, these will be documented in a protocol amendment.

For the purpose of analysis, the end of study is defined as the date of final database lock.

All variables will be summarized at specified time points by dose level. Categorical variables will be summarized using counts (n) and percents (%) and will be presented in the form n (%). Continuous variables (eg, height, weight) will be summarized using the number of observations, mean, standard deviation and/or standard error, and minimum and maximum values.

### **8.1 Analysis Populations**

The following subject subsets will be defined for this study.

- Intent to Treat (ITT) population: the set of all randomized subjects who have received at least one dose of study treatment. Efficacy analyses will be

performed on subjects from this population. Subjects in the ITT population will be assigned to the treatment to which they were randomized, regardless of the treatment they actually received.

- Safety population: the set of subjects who received at least 1 dose of study drug and have at least 1 safety assessment. All safety analyses, including analyses of AEs, clinical laboratory results, vital signs, and physical examinations will be conducted on the Safety population. Subjects in the safety population will be assigned to the treatment they actually received, regardless of the treatment to which they were randomized.
- PK population: The set of subjects who receive at least 1 dose of study drug and who have sufficient post-dose blood samples taken to contribute to the sparse PK sampling analysis. Subjects in the PK population will be assigned to the treatment they actually received, regardless of the treatment to which they were randomized.

## **8.2 Statistical Methods**

### **8.2.1 Subject Disposition**

The disposition of subjects at all scheduled visits will be determined on the basis of evaluations made at each visit. The disposition will be summarized by treatment group.

### **8.2.2 Demographics and Baseline Characteristics**

Demographics and subject characteristics obtained at the baseline evaluation, including age, genotype, race, ethnicity, weight, and hemoglobin electrophoresis results, will be summarized descriptively using the ITT population.

### **8.2.3 Efficacy Analysis**

The efficacy analysis will be performed on the ITT population. Study site and subject age will be included in the model as permitted by sample size.

#### **8.2.3.1 Primary Efficacy Analysis**

The primary efficacy endpoint is the time to resolution of VOC from the time the subject receives his or her first dose. Resolution of VOC is defined as the first of the following to occur:

- Sustained decrease in pain score of at least 1.5 cm out of 10 cm since baseline; AND transition to oral pain medications per hospital procedures (subject is on no IV pain medications),
- OR readiness for discharge as stated by the physician and subject,
- OR discharge to home.

The null hypothesis of no difference in time to resolution of VOC between active and placebo treatment groups will be evaluated by using the F-test from an

analysis of covariance (ANCOVA) model, controlling for sex, age and Hemoglobin A level. No censoring is anticipated as the time to discharge will be known for all subjects. Inferential testing will be performed using a fixed-sequence testing procedure.

### **8.2.3.2 Secondary Efficacy Analysis**

Comparisons of time to reduced pain score by at least 1.5 out of 10 cm from the baseline value and time to transition to oral pain medications between the active and placebo treatment groups will be presented by Kaplan-Meier plots stratified by treatment group. The survival distribution will be compared by log-rank test. If there is no censoring in these outcomes, the ANCOVA model similar to the analysis for time to resolution of VOC will be used instead.

The effects of study drug on time to readiness for discharge and time to discharge will also be summarized by treatment group and evaluated by ANCOVA model, controlling for sex and age. Time to readiness for discharge as noted by the subject alone, by the physician alone, and by both the subject and physician, will be considered.

The cumulative amount of IV analgesic use (opioid and NSAID) from admission to discharge will be standardized using morphine equivalents. This amount will be compared between active and placebo treatment groups by an ANCOVA model, controlling for age and sex. The hourly IV analgesic usage over time will be modeled longitudinally using a linear mixed model with subject as a random effect and treatment group, time, sex and age as fixed effects.

The intensity of pain as measured by VAS will be analyzed longitudinally using a linear mixed model with subject as a random effect and treatment group, time, sex, age, and baseline pain score as fixed effects.

The differences in percentage of subjects with complications of VOC including acute chest syndrome, transfusion, stroke and death between active and placebo treatment groups will be tested using Mantel-Haenszel Chi-Square test or Fisher's Exact test, depending on the number of subjects with events.

The mean hsCRP value and mean change from baseline value will be summarized at each time point. If the normal ranges are different among sites, the standardized values will be presented. The difference in values between treatment groups will be analyzed using a linear mixed model with subject as a random effect and treatment group, time, sex, age and baseline measurement as fixed effects.

The results from IV antibiotic usage will be presented in listings. ICU stay and transfusion data including frequency, timing related to VOC and diagnosis leading to transfer to ICU (leading to transfusion) will also be presented in listings.

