### 3 STUDY DESIGN

This is a randomized, double-blind, placebo-controlled trial of multiple IV doses of GMI-1070 or placebo in subjects hospitalized for sickle cell VOC. Investigators are encouraged to identify subjects with VOC who are likely to be admitted, and approach them for consent and eligibility criteria early in the process of treatment for VOC. All subjects should be dosed with study drug within 24 hours of first medical evaluation in the Emergency Department/clinic.

In addition, investigators are encouraged to identify those subjects who may be appropriate for the study before they develop VOC. These subjects may be approached with educational information about the study. Such education will not replace the need to obtain informed consent at the time of hospitalization for VOC.

The study will enroll until approximately 76 evaluable subjects (defined as those who have received at least 1 dose of study medication) have been enrolled. During Visit 1, eligible subjects will be randomized in a 1:1 ratio to either GMI-1070 or placebo using an IVRS. Study drug will be administered as a loading dose of 40 mg/kg followed by 20 mg/kg every  $12 \pm 2$  hours until the subject meets criteria for improvement of pain, or up to 7 days of treatment (maximum 15 doses including the loading dose), whichever comes first. If the subject has no improvement in VOC after 5 days (eg, no change in VAS and no decrease in IV pain medication requirement), study drug should be discontinued.

Resolution of VOC is defined as the first of the following to occur:

- Sustained decrease in pain score of at least 1.5 cm out of 10 cm since baseline; AND transition to oral pain medications per hospital procedures (subject is on no IV pain medications),
- OR readiness for discharge as stated by the physician and subject,
- OR discharge to home.

For the purposes of this study, ‘sustained’ is defined as 2 consecutive pain scores at least 4 hours apart as reported by the subject on a VAS; ‘baseline’ is defined as the pain score just prior to the first dose of study drug as reported by the subject on the VAS.

Visits for follow-up examinations will be made  $36 \pm 12$  hours post last dose (Visit 2) (ideally this will occur prior to discharge from the hospital), on day  $7 \pm 3$  post last dose (Visit 3), and on day  $28 \pm 5$  post last dose (Visit 4).

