### **4.2 Inclusion Criteria**

To be eligible for inclusion, each subject must fulfill each of the following criteria at screening, and must continue to fulfill these criteria prior to dosing:

1. 12 to 60 years of age
2. Confirmed diagnosis of sickle cell disease (HbSS or HbS- $\beta^0$ thalassemia)
3. Diagnosis of VOC at the time of enrollment
4. Hospitalized or in process of admission at the time of enrollment
5. Able to receive the first dose of study drug within 24 hours of initial medical evaluation in the Emergency Department/clinic for VOC;
  - Subjects treated as an outpatient within the past 48 hours for the same VOC episode may be enrolled if dosing is also expected within 24 hours of their second (admitting) presentation.
6. Documented and observed written informed consent (and assent, where applicable)

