### **5.2.1 Pain Management**

Pain management should be approached according to the institution's usual procedures, with the following suggestions for standardized management:

- Recommended IV pain medications include morphine (preferred), hydromorphone, ketorolac, or fentanyl, used in accordance with standard clinical practice
- Initial treatment should aim to achieve pain control; pain control is defined as pain that does not require further escalation of pain medication OR subject reports pain is controlled
- Ongoing treatment should aim to maintain pain control; consider weaning IV opioids once pain is controlled ( $\leq 7/10$ )
- Discharge criteria related to pain may include improved pain score; on oral hydration; and on oral pain medications for at least 6 hours
- Patient-controlled analgesia (PCA) use (basal and bolus dosing) is encouraged for all subjects, per hospital procedure
- Subjects will be adequately hydrated per routine procedure and as medically indicated

Discharge instructions for pain management should include a minimum of 48 hours continuous treatment with oral opioid or similar pain medications. Subjects on chronic opioids may require different instructions, such as an opioid weaning regimen.

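### One secondary analgesic outcome is summed from admission rather than first dose, with no pre-dose adjustment and with NSAIDs on an opioid scale: this dilutes the effect and adds noise, but does not bias the arms

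*Protocol*

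**What the plan says.** Section 8.2.3.2 of the protocol defines the outcome: "The cumulative amount of IV analgesic use (opioid and NSAID) from admission to discharge will be standardized using morphine equivalents". It then fixes the comparison: "This amount will be compared between active and placebo treatment groups by an ANCOVA model, controlling for age and sex". A companion analysis follows: "The hourly IV analgesic usage over time will be modeled longitudinally using a linear mixed model with subject as a random effect", with treatment, time, sex and age as fixed effects and no stated time origin.

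The primary endpoint in Section 8.2.3.1 uses a different clock: "The primary efficacy endpoint is the time to resolution of VOC from the time the subject receives his or her first dose".

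On timing, Section 4.2 admits subjects who are "Hospitalized or in process of admission at the time of enrollment", and Section 3 says "All subjects should be dosed with study drug within 24 hours of first medical evaluation in the Emergency Department/clinic". On drugs, Section 5.2.1 reads "Recommended IV pain medications include morphine (preferred), hydromorphone, ketorolac, or fentanyl", so some IV NSAID use is expected. Sections 6.2 and 6.5.1 name IV opioid and IV NSAID use as two separate items.

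In the same Section 8.2.3.2, the VAS model includes the baseline pain score and the hsCRP model includes the baseline measurement. The synopsis lists amount and duration of IV analgesics first among the clinical-activity endpoints but does not rank it.

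**The concern.** A subject already admitted when enrolled receives IV analgesics that study drug cannot influence until the first infusion starts. Under the stated window that use enters the outcome in both arms. The expected difference between arms stays the same, but it is measured against a larger total with more spread. Pre-dose use would be the natural baseline covariate, as the VAS and hsCRP models treat theirs; here it sits inside the outcome.

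A second, separate difficulty is the scale. Morphine equivalence is an opioid scale. Once NSAIDs are converted and added, a change in the total is no longer a change in opioid use, and a shift between drug classes can hide or mimic opioid sparing.

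At stake is the precision and readability of one secondary outcome, in a trial with about 38 subjects per arm. The primary analysis is not affected.

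**Working it through.** **1. The plan's own sizing.** Section 8.3.2 gives a placebo mean of 103 h, SD 60 h, 38 per group and two-sided alpha 0.045. The standard error is 60 × √(2/38) = 13.76 h. A 40% decrease is 0.40 × 103 = 41.2 h, noncentrality 41.2/13.76 = 2.99, and the two-sample t-test has 82.8% power (stated: 83%). A 43.8% decrease is 45.1 h, noncentrality 3.28, power 89.0% (stated: 89%). Both reproduce. The protocol gives no mean, SD or power for analgesic use, so the rest is illustration.

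**2. Dilution.** Assume post-dose use is proportional to the 103 h duration and the drug removes 40% of it. Let L be the hours from admission to first dose, and r the pre-dose hourly rate relative to the post-dose rate.

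- Pre-dose share of the placebo total = rL/(103 + rL)
- Apparent reduction = 41.2/(103 + rL)

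| L | r = 1 | r = 2 | r = 3 |
|---|---|---|---|
| 0 h | 40.0% | 40.0% | 40.0% |
| 6 h | 37.8% | 35.8% | 34.0% |
| 12 h | 35.8% | 32.4% | 29.6% |
| 24 h | 32.4% | 27.3% | 23.5% |

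L is not given. It is near zero for a subject dosed while being admitted and at most about 24 h otherwise.

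**3. Two middle cases, with r = 1.5.**

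- Lead spread evenly over 0 to 6 h (mean 3 h): 41.2/(103 + 1.5 × 3) = 41.2/107.5 = 38%.
- Lead spread evenly over 4 to 24 h (mean 14 h): 41.2/(103 + 1.5 × 14) = 41.2/124 = 33%.

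**4. Power.** Simulation with post-dose use = rate × duration; rate CV 0.7; duration mean 103 h, SD 60 h, 40% shorter on active; pre-dose use = pre-dose rate × lead, at 1.5 times the post-dose rate; 38 per arm; alpha 0.045; leads as in step 3; pre/post rate correlation 0, 0.5 or 0.9.

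| Analysis | Power across scenarios |
|---|---|
| From admission | about 48-59% |
| From first dose | about 57-60% |
| From first dose, adjusted for pre-dose rate | about 58-80% |

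Moving the start to first dose gains about 0 to 9 points. The covariate then adds about 0 points at correlation 0, 4 at 0.5 and 20 at 0.9. At worst, the combined change costs about half a point.

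**5. NSAID scale.** Write the total as T = O + fN, where O is opioid in morphine equivalents, N is NSAID amount and f the conversion factor. If a subject uses ΔO less opioid and ΔN more NSAID, T changes by −ΔO + fΔN. That equals the opioid change only if f = 0 or NSAID use is unchanged. A published f would make T computable, but would not make it a measure of opioid use.

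**The case against.** The case for leaving the plan alone has real strength.

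- **No bias.** Pre-dose use precedes treatment and is balanced in expectation, and the absolute difference is unchanged. A reader might infer that the comparison is invalid or favours an arm; the documents do not support that. This stands in full.
- **The lead may be short.** A reader might take the 24 h limit as the length of the pre-dose window. It runs from first medical evaluation, not admission. Subjects may enroll while still being admitted, and Section 6.1.1 asks sites to expedite admission for early enrollment. Emergency-department use before admission falls outside a sum that starts at admission. With a short lead the loss is a few points at most. This also stands.
- **Status of the outcome.** It is tempting to call this the main clinical-activity outcome. The protocol ranks none of these endpoints, and the order of its fixed-sequence procedure is not given.
- **The largest power gain comes from the covariate**, and only if pre- and post-dose use are strongly correlated. Omitting a precision covariate is not an error in itself. True, but the same section adjusts for baseline in two neighbouring models.
- **Whole-stay use is a legitimate descriptive quantity**, and hourly use is also modelled. The hourly model states no time origin and has no baseline-use term, so it does not resolve the issue.
- **Conversion factors belong in the SAP**, which is not shown. Agreed: their absence is no finding. The combined sum, however, is fixed in the protocol. Nor is NSAID use beyond the drug's reach; after first dose it can respond to treatment, which is why the scale is a separate point from the window.

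**Conclusion.** The point holds as a matter of efficiency and interpretability for one unranked secondary outcome. The window, the combined scale and the covariates are stated choices, not details left open.

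Where subjects are admitted before first dose, the total dilutes the relative effect and adds variance. In the two illustrated cases 40% becomes about 38% or 33%, and power is about 48-59% rather than the 57-60% obtained from first dose. With adjustment for pre-dose rate it is 58-80%. These figures rest on assumed rates, leads and correlations, and on applying alpha 0.045 to this outcome; only the duration mean and SD, the 40% effect, the group size and the alpha come from the protocol. The upper end needs pre- and post-dose use to be strongly correlated. Heavy use over a full 24 h lead would dilute more (step 2), and a lead near zero would leave almost no effect.

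The documents do not support a claim of bias between arms, or of a threat to the primary result.

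**What to change.** In Section 8.2.3.2:

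1. Define the compared outcome as cumulative IV opioid use, in morphine equivalents, from the start of the first study-drug infusion to discharge.
2. Add pre-dose IV opioid use per hour as a covariate beside age and sex, matching the baseline terms in the VAS and hsCRP models.
3. Summarize IV NSAID use separately, without conversion to morphine equivalents.
4. Keep the admission-to-discharge total, if wanted, as a descriptive summary.

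No new data are needed. Section 6.1.3 records infusion start and end times, and Section 5.2 records concomitant treatments from within 48 hours of randomization. The cost is a wording change, one more derived variable and one degree of freedom.
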